### **3.2    General definitions**

The term study drug or investigational treatment refers to LRX712 or Placebo, while the term investigational drug refers exclusively to LRX712.

#### **Date of first administration of investigational drug**

The date of last administration of investigational drug is defined as the last date when a nonzero dose of investigational drug is administered and recorded on dose administration (e)CRF. The date of last administration of investigational drug will also be referred as end of investigational drug or end of investigational treatment.

#### **Study day**

Study day 1 for all assessments is taken to be the start of investigational treatment.

The study day for all assessments will be calculated as follows:

1. If date of assessment occurred on or after the start of investigational treatment, then Study day = Date of assessment - Start of investigational treatment + 1.
2. If date of assessment occurred before the start of investigational treatment, then Study day = Date of assessment - Start of investigational treatment.

The study day will be displayed in the data listings. If an event starts before the reference start date, the study day displayed on the listing will be negative.

## Baseline

For safety evaluations, the last available assessment on or before the date of start of investigational treatment is taken as “baseline” assessment. In case time of assessment and time of treatment start is captured, the last available assessment before the treatment start date/time is used for baseline.

For safety parameters (e.g. ECGs), where the study requires multiple replicates per time point, the average of these measurements would be calculated (if not already available in the database) before determining baseline.

In rare cases where multiple measurements meet the baseline definition, with no further flag or label that can identify the chronological order, then the following rule should be applied: If values are from central and local laboratories, the value from central assessment should be considered as baseline. If multiple values are from the same laboratory (local or central) or collected for ECGs or vital signs, then the last value should be considered as baseline.

If participants have no value as defined above, the baseline result will be missing.

For safety parameters other than ECG, scheduled pre-dose collections as well as unscheduled collections on Day 1 for which no time is available will be considered as pre-dose.

For ECG, study Day 1 scheduled pre-dose ECGs will be considered to have been obtained prior to start of investigational treatment if dosing time or ECG time is missing and used in the calculation of the baseline value. If a scheduled pre-dose measurement actually occurred post-dose, then the corresponding measurement will be treated and analyzed similar to an unscheduled post-dose measurement.

Regarding MRI, baseline is defined as the scan performed between Day -45 to -2.

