Subjects who meet the eligibility criteria at screening will be admitted for Day 1 evaluations. Study sites may choose to admit subjects overnight on Day -1 and from Day 1 to Day 2, due to the extensive assessment schedule and organizational purposes.

To mitigate potential SARS-CoV-2 infections among subjects, guidance and requirements provided by the local regulatory authorities will be followed (e.g., subjects will be screened for SARS-CoV-2 by PCR or equivalent approved methodology prior to admission at the study site for any overnight stays following local site-specific SOPs).

The study consists of 3 periods:

Screening (Day -45 to Day -6)

Informed consent will be obtained prior to undertaking any study specific procedures. The Screening epoch begins at Day -45 and ends with randomization between Day -5 to Day -1.

All entry criteria must be fulfilled before randomization (and latest on Day -6). In the case where a safety laboratory assessment at Screening is outside of the range specified in the exclusion criteria, the assessment may be repeated once prior to randomization. If the repeat value remains outside of the specified ranges, the subject must be excluded from the study.

It is recommended to perform simple Screening assessments first (e.g., medical history, 12-lead digitized ECG, vital signs, age, body mass index, etc.) to identify non-eligible subjects early, followed by laboratory samples, which require shipping and analysis. Finally, the X-ray examination should confirm the radiographic presence of OA and fmJSW in the 1.5-3.5 mm range for females, and 2-4 mm range for males (based on normative values of 4.1-5.5 for women and 4.9-6.5 for men ([Beattie et al 2008](#)) at the x=0.225 fixed point of the medial tibio-femoral compartment ([Neumann et al 2009](#))).

MRI examination is performed during the Screening period after verifying that none of the previous Screening tests precludes study eligibility.

Due to the extensive preparation of study medication, the randomization may be performed the days before study drug administration on Day 1 (Day -5 to Day -1), once eligibility is confirmed and as near to Day 1 as possible. The reference for visit scheduling throughout the study will be Day 1. Eligible subjects will be randomized in a 1:1:1 ratio to either i.a. LRX712 15 mg, LRX712 25 mg, or placebo.

Please see the SOM for further details on Screening assessments.

Treatment (8 weeks)

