8.1 Screening

It is permissible to **re-screen** a subject if s/he fails the initial screening; however, each case must be discussed and agreed with the Sponsor on a case-by-case basis, a **new Screening number** assigned, and a **new written informed consent signed** by the subject and investigator.

In the case that a safety laboratory assessment at Screening and/or baseline is outside of the range specified in the exclusion criteria, the assessment may be repeated once prior to randomization. If the repeat value remains outside of the specified ranges, the subject must be excluded from the study.

Re-screening is permitted if the reason(s) for failing the initial screening were unrelated to the knee X-ray. The subject will not need to undergo another knee X-ray and the initial one may be used for re-screening purposes, if re-screening occurs within 6 months of the X-ray date. Likewise, the subject will not need to undergo another knee 7T MRI and the initial imaging may be used for rescreening purposes, if rescreening occurs within three months of the original 7T MRI date. The objective of this measure is to avoid unnecessary radiation exposure, given that meaningful radiologic changes are not likely to occur during the period of re-screening.

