#### **4.1 Primary objective**

The primary objective of this study is to assess the efficacy of q4w x 3 i.a. injections of LRX712 in restoring the morphometrics of articular cartilage in the medial femoral condyle (MFC). To this end, a statistical analysis will be done to compare the change in medial femoral condyle cartilage volume in the index region measured by 7T MRI from baseline to week 28 in LRX712 vs. placebo –treated subjects.

Baseline refers to data collected at Screening for the imaging assessments (Day -45 to -2).

Medial femoral condyle is defined as sum of the International Cartilage Regeneration Society (ICRS) sub-regions MAC, MCC, and MPC. See [Table 4-1](#).

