#### **4.1.4 Handling of missing values/censoring/discontinuations**

Some intermittently missing data may be expected due to participants occasionally missing a study visit while continuing with the randomized treatment. Such data will be implicitly imputed by the MMRM under the MAR assumption. Only participants with a baseline and at least one post-randomization measurement will be included in the primary analysis.

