### **4.2 Secondary objectives**

There are two secondary objective related to efficacy:

- To assess the efficacy of q4w x 3 i.a. injections of LRX712 in regenerating the articular hyaline cartilage composition in the medial femoral condyle
- To assess the efficacy of q4w x 3 i.a. injections of LRX712 in restoring the morphometrics of articular cartilage in the medial femoral condyle

Baseline is defined as scan performed between Day -45 to -2.

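### The SAP's MRI baseline window (Day -45 to -2) does not cover a 7T scan reused under Protocol 8.1 that is more than 45 days old at Day 1, so a compliant re-screened participant could be excluded from the primary analysis

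*SAP*

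**What the plan says.** The SAP fixes the MRI baseline by day in three places.

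- SAP 3.2, under Baseline: "Regarding MRI, baseline is defined as the scan performed between Day -45 to -2".
- SAP 4.1, for the primary endpoint: "Baseline refers to data collected at Screening for the imaging assessments (Day -45 to -2" (the closing bracket is omitted here).
- SAP 4.2, for the secondary MRI endpoints: "Baseline is defined as scan performed between Day -45 to -2".

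Days are counted from dosing: "Study day 1 for all assessments is taken to be the start of investigational treatment".

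Protocol 8.1 deals with re-screening. It says "Likewise, the subject will not need to undergo another knee 7T MRI" and that "the initial imaging may be used for rescreening purposes, if rescreening occurs within three months of the original 7T MRI date". The protocol's screening period (Section 3.2) is "Screening (Day -45 to Day -6" (closing bracket again omitted).

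SAP 4.1.4 sets the entry condition for the primary analysis: "Only participants with a baseline and at least one post-randomization measurement will be included in the primary analysis". SAP 4.1.1 makes change from baseline the outcome and also includes baseline as a fixed effect in the MMRM.

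**The concern.** The protocol's three-month limit runs from the scan to re-screening. The SAP's 45-day limit runs from the scan to first dose. Someone can satisfy the first and fail the second. That participant would follow the protocol, receive all three injections and provide every later scan, yet have no value the SAP recognises as an MRI baseline. No change from baseline could be formed for volume, thickness or sodium content.

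The exclusion looks unintended. SAP Table 3-1 names only an informed-consent deviation as a reason to remove anyone from the PD analysis set. This participant would therefore belong to the PD set and then fall out through a date window. Protocol 9.1.2 replaces discontinued subjects, so a completer lost in this way would not be replaced under it.

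Two things are at stake. One is a small loss of precision in a trial planned on 13 completers per arm. The other is that, if the gap comes to light only at analysis, someone must decide then whether the participant counts. Protocol 6.4 gives the study statistician access to the randomization list from the start, so that decision could be made by someone who knows the allocation.

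**Working it through.** **1. How old can a reused scan be at Day 1?**

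Inputs: the three-month reuse limit (Protocol 8.1), taken as 90 to 92 days, and the screening period of Day -45 to Day -6 (Protocol 3.2).

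Age at Day 1 = days from scan to re-screening + days from re-screening to Day 1.

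- Re-screening at the three-month limit, shortest screening: 90 + 6 = 96 days.
- Re-screening at the three-month limit, longest screening: 90 + 45 = 135 to 92 + 45 = 137 days, or about 91 + 45 = 136.

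**2. Which reused scans fall inside the SAP window?**

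Under the SAP's study-day rule, a scan taken A days before Day 1 has study day -A. It qualifies if A lies between 2 and 45.

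| Scan age at Day 1 (days) | Study day | Inside Day -45 to -2? |
|---|---|---|
| 45 | -45 | Yes |
| 46 | -46 | No |
| 60 | -60 | No |
| 90 | -90 | No |
| 135 | -135 | No |

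The conflict covers reused scans from 46 to about 136 days old.

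**3. Does any other SAP rule supply a baseline?**

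The last-available-assessment rule in SAP 3.2 is limited to safety evaluations. MRI has only the day window, and the SAP does not mention reused scans. The exclusion then follows from SAP 4.1.4 and the model in 4.1.1. SAP 4.2 carries the same window to the secondary endpoints.

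**4. Can the case arise?**

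Protocol 3.2 and a footnote to Table 8-1 place the MRI after the other eligibility checks, so most screen failures will come before any scan. Some checks come later. Clinically relevant effusion and QTcF are assessed again on Day 1 (Protocol 5.2, criteria 7 and 17). Protocol 8.4.6 postpones enrolment for COVID-19 symptoms or a positive test in the week before first dosing, and allows re-screening afterwards.

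**5. What would a loss cost?**

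Inputs (Protocol 12.8.1, SAP 7): difference 123 mm³, SD 130 mm³, 13 per arm, two-sided alpha 0.10.

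Noncentrality = 123 / (130 × √(1/n₁ + 1/n₂)), with n₁ + n₂ - 2 degrees of freedom.

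For 13 v 13: 130 × √(2/13) = 50.99, and 123 / 50.99 = 2.412. The normal approximation gives Φ(2.412 - 1.645) = 77.9%, which matches the SAP's 78%. The noncentral t with 24 degrees of freedom gives 75.8%, consistent with the protocol's approximate 75%.

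The documents do not give the number affected. Taking 0 to 3 as an assumption:

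| Analysed in one comparison | Number lost | Power, t | Power, normal |
|---|---|---|---|
| 13 v 13 | 0 | 75.8% | 77.9% |
| 12 v 13 | 1 | 74.2% | 76.4% |
| 12 v 12 | 2, one per arm | 72.6% | 74.9% |
| 11 v 13 | 2, same arm | 72.3% | 74.7% |
| 10 v 13 | 3, same arm | 70.2% | 72.7% |

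The first loss costs 75.8 - 74.2 = 1.6 points, and one participant is 1/13, about 8%, of an arm's planned completers. Placebo is the comparator for both doses, so a lost placebo participant gives 13 v 12 in both comparisons.

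**The case against.** The strongest reply is that the situation is rare and that the day range is only a visit label. Protocol 3.2 defines imaging baseline as what was collected at Screening, with no day limit, and SAP 4.1 uses similar words with the days in brackets. The SAP window ends at Day -2 while protocol screening ends at Day -6, which suggests loose drafting. On that reading, a scan accepted under Protocol 8.1 simply is the Screening scan. Re-screening also needs the sponsor's agreement case by case and is not open to those who failed on the X-ray.

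The point about rarity stands. The participant must pass the earlier checks, be scanned, fail late, be re-screened without a new scan, and be dosed more than 45 days after the scan. The label reading does not settle the matter, because SAP 3.2 refers to the day on which the scan was performed and offers no alternative.

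A second reply is that a recent baseline is worth protecting. This has force. A scan at Day -45 precedes the nominal Week 28 scan (Day 197) by 45 + 196 = 241 days. One taken 136 days before dosing precedes it by 136 + 196 = 332 days. Protocol 8.1 does not forbid a repeat scan, so requiring one when the first would fall outside the window would also remove the conflict.

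A reader might infer that every re-screened participant who reuses a scan is dropped. The documents do not support that, since a reused scan 2 to 45 days old at Day 1 meets the SAP definition.

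**Conclusion.** The two documents conflict for reused scans more than 45 days old at Day 1. Read literally, the SAP would exclude a protocol-compliant participant from the primary analysis and leave the secondary MRI endpoints without a baseline.

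The effect is conditional and small: about 1.6 power points for the first participant lost from a comparison, and slightly more for each further one. The figures assume exactly 13 analysable participants per arm. They also ignore the three placebo participants from before Amendment 4 who are to be pooled with the control group. Scan date and first dose are set without regard to treatment response, so the literal rule mainly costs precision. An ad hoc ruling at analysis is the less comfortable prospect.

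A reader might also infer that participants have already been lost, or that the primary result is compromised. The documents give no count of re-screened participants or reused scans, and the number affected may be zero. The point is worth correcting because the rule decides who enters the primary analysis and is easily put right beforehand.

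**What to change.** In SAP 3.2, 4.1 and 4.2, define MRI baseline as the last 7T MRI before the first injection, including a scan reused under Protocol 8.1. List participants whose baseline scan predates Day -45. If there are any, repeat the primary analysis without them as a sensitivity analysis.

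The same edit removes the mismatch between the SAP's Day -2 limit and the protocol's Day -6 end of screening.

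The cost is one sentence in each of three SAP sections, one listing and possibly one extra model run, with no change to trial conduct. The downside is that some baselines could be up to 136 - 45 = 91 days, about three months, older than the SAP now allows. The sensitivity analysis shows whether that matters. If the sponsor prefers to keep the 45-day limit, the alternative is to amend Protocol 8.1 so that it agrees with the SAP, at the price of a protocol amendment and additional scans.

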## On-treatment assessment/event

The overall observation period will be divided into three mutually exclusive segments:

1. ***pre-treatment period:*** from day of participant’s informed consent to before date of first administration of investigational treatment
2. ***on-treatment period:*** from date of first administration of investigational treatment to 28 days after date of last administration of investigational treatment (including start and stop date)
3. ***post-treatment period:*** starting at day 29 after last administration of investigational treatment.

*Note:* If dates are incomplete in a way that clear assignment to pre-, on-, post-treatment period cannot be made, then the respective data will be assigned to the on-treatment period.

Safety summaries (tables, figures) include only data from the on-treatment period with the exception of baseline data which will also be summarized where appropriate (e.g. change from baseline summaries). In particular, summary tables for adverse events (AEs) will summarize only on-treatment events, with a start date during the on-treatment period (**treatment-emergent** AEs).

However, all safety data (including those from the post-treatment period) will be listed and those collected during the post-treatment period will be flagged.

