Adverse events (including lab abnormalities that constitute AEs) should be described using a diagnosis whenever possible, rather than individual underlying signs and symptoms.

Abnormal laboratory values or test results constitute adverse events only if they fulfill at least one of the following criteria:

- they induce clinical signs or symptoms
- they are considered clinically significant
- they require therapy

Clinically significant abnormal laboratory values or test results must be identified through a review of values outside of normal ranges/clinically notable ranges, significant changes from baseline or the previous visit, or values which are non-typical in subjects with the underlying disease. Alert ranges for laboratory and other test abnormalities are included in [Appendix 1](#).

Adverse event monitoring should be continued for at least 30 days (or 5 half-lives or end of study visit, whichever is longer) following the last dose of study treatment. In order to ensure adequate and efficient safety monitoring, the following activities will be considered for documentation:

1. From enrollment until Week 28 (included), any AE will be reported as per instructions described above
2. From Week 28 until Week 52, only the AEs of special interest listed below and any local procedure performed in the index knee (i.e., arthroscopy or surgery), will be reported, alongside any associated prescription medications, over-the-counter drugs and significant non-drug therapies (including physical therapy and blood transfusions).

These are defined as follows:

- a. Any adverse event in the index knee linked to symptoms and/or signs of pain, dysfunction, local inflammation (warmth or swelling, e.g.) or stiffness
- b. Any adverse event that may be related or is the result of events mentioned in the previous bullet point i.e., a fall caused by sudden pain and related dysfunction in the index knee
- c. Any adverse event, which in the investigator's opinion is related to the medical condition of the index knee

Once an adverse event is detected, it must be followed to resolution or until it is judged to be permanent (e.g., continuing at the end of the study), and assessment must be made at each visit (or more frequently, if necessary) of any changes in severity, the suspected relationship to the interventions required to treat it, and the outcome.

Information about adverse drug reactions for the investigational drug can be found in the Investigator's Brochure (IB).

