12.5.2 Safety endpoints

For all safety analyses, the safety set will be used. All listings and tables will be presented by treatment group.

Adverse events

The number (and percentage) of subjects with treatment emergent adverse events (events started after the first dose of study medication or events present prior to start of double-blind treatment but increased in severity based on preferred term) will be summarized in the following ways:

- by treatment, primary system organ class and preferred term.
- by treatment, primary system organ class, preferred term and maximum severity.
- by treatment, Standardized MedDRA Query (SMQ) and preferred term.

Separate summaries will be provided for study medication-related adverse events, deaths, serious adverse events, or other significant adverse events leading to discontinuation.

A subject with multiple adverse events within a primary system organ class is only counted once towards the total of the primary system organ class.

To assess local tolerability of LRX712 with multiple injections, the probability of an injection site adverse event will be calculated for each treatment group. A Bayesian Poisson regression model will be fitted with treatment group as fixed categorical variable. Further details on the definition of injection site adverse events is given in the SAP.

Vital signs

All vital signs data will be listed by treatment group, subject, and visit/time, and if ranges are available, abnormalities (and relevant orthostatic changes) will be flagged. Summary statistics will be provided by treatment and visit/time.

12-lead digitized ECG

A standard 12-lead electrocardiogram will be performed in triplicate:3 tracings of at least 10 sec duration to be obtained within a 2-5 min window). A standard 12-lead electrocardiogram will be performed in triplicate (3 tracings of at least 10 sec duration to be obtained within a 2-5 min window.

1. PR, QRS, QT, QTcF, and RR intervals will be obtained from 12-lead ECGs for each subject during the study. ECG data will be read and interpreted locally.
2. Categorical Analysis of QT/QTc interval data based on the number of subjects meeting or exceeding predefined limits in terms of absolute QT/QTc intervals or changes from baseline will be presented. In addition, a listing of these subjects will be produced by treatment group.

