### **5 Safety analyses**

All safety analyses will be based on the Safety set unless otherwise specified. Safety summaries include only on-treatment assessments (refer to [Section 3.2](#)); safety listings include all assessments with those more than 28 days after last investigational treatment flagged.

Safety assessments include AEs, laboratory data, vital signs, deaths and ECGs. All Section 16 safety listings are presented using the Safety Analysis Set, and Section 14 using Safety set unless otherwise specified. The Safety Analysis Set will be used for all safety summaries. Safety summaries include only on-treatment assessments (refer to [Section 3.2](#)), with a start date during the on-treatment period (treatment-emergent AEs).

For selected items, change from baseline summaries generated for laboratory values, ECG, vital signs may use data before start of investigational treatment for baseline calculations.

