#### **5.1 Adverse event (AEs)**

All information obtained on adverse events will be displayed by treatment and participant.

The number (and percentage) of participants with treatment emergent adverse events (events started after the first dose of the study medication or events prior to start of the treatment but increased in severity based on the preferred term) will be summarized by treatment, primary system organ class and preferred term, and maximum severity.

Separate summaries will be provided for study medication related adverse events, death, serious adverse events, other significant adverse events leading to discontinuation.

A participant with multiple adverse events within a primary system organ class is only counted once towards the total of the primary system organ class.

If, for the same participant, several consecutive AEs (irrespective of start treatment causality, seriousness and severity) occurred with the same SOC and PT:

- A single occurrence will be counted if there is  $\leq 1$  day gap between the end date of the preceding AE and the start date of the consecutive AE.
- More than one occurrence will be counted if there is  $> 1$  day gap between the end date of the preceding AE and the start date of the consecutive AE.

For occurrence, the presence of at least one SAE has to be checked in a block e.g. among AEs in a  $\leq$  day gap block. If at least one SAE is occurring, then one occurrence is calculated for that SAE.

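### The SAP closes its AE tables 28 days after the last dose, so later AEs that protocol 12.5.2 would tabulate get no by-arm count in the visible plan

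*SAP*

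**What the plan says.** SAP 3.2 (On-treatment assessment/event) splits follow-up into three periods. The on-treatment period runs "from date of first administration of investigational treatment to 28 days after date of last administration of investigational treatment", both ends included. All safety summaries are confined to that period, apart from baseline values, and for AEs the rule is spelled out: "summary tables for adverse events (AEs) will summarize only on-treatment events, with a start date during the on-treatment period". One default is given: "If dates are incomplete in a way that clear assignment to pre-, on-, post-treatment period cannot be made", the data count as on-treatment. SAP 5 repeats the restriction and adds that "safety listings include all assessments with those more than 28 days after last investigational treatment flagged".

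Protocol 12.5.2 defines the tabulated events differently: "events started after the first dose of study medication or events present prior to start of double-blind treatment but increased in severity". It gives no end date. SAP 5.1 carries over almost the same definition: "events started after the first dose of the study medication or events prior to start of the treatment but increased in severity". For vital signs, protocol 12.5.2 says that "Summary statistics will be provided by treatment and visit/time", and it says the same for ECG and laboratory data, without limiting the visits.

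Collection runs much longer than 28 days. Protocol 10.1.1.1 has every AE reported up to and including Week 28, then index-knee AEs of special interest and index-knee procedures to Week 52. Protocol 10.1.3 has SAEs reported to the last study visit. Protocol 8.4.4 sets calls at Weeks 32 and 42 to gather AEs of special interest and SAEs.

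**The concern.** Safety and local tolerability of repeated injections is a secondary objective (SAP 1.3), and the protocol goes to some trouble to follow the index knee for a year. The question for the report is whether late knee events or SAEs differ by arm. If the SAP is followed as written, no visible table answers that. A reader would have to tally events from listings and supply the denominators.

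There are two further effects. The SAP counts a pre-existing event that worsens after dosing as treatment-emergent in 5.1, but the start-date rule in 3.2 and 5 shuts it out, because its start date precedes the first dose. Two programmers could build different tables from the same text. In addition, the restriction in SAP 3.2 covers all safety tables and figures, so it reaches the by-visit summaries as well.

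**Working it through.** Inputs: dosing on Days 1, 29 and 57 (protocol 6.1.3); Week 16 visit on Day 113 ± 7, Week 28 visit on Day 197 ± 7, end of study on Day 364 + 30 (protocol Table 8-1); 28-day window (SAP 3.2).

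The plan's own days reproduce: the third dose is 1 + 2 × 28 = Day 57, and Week 28 is 1 + 28 × 7 = Day 197.

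The last tabulated onset day is the last dose day + 28. The untabulated part of all-AE collection is 197 minus that day:

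| Doses received | Tables close | Onset days not tabulated, to Day 197 |
|---|---|---|
| 3 | 57 + 28 = Day 85 | 197 − 85 = 112 (112/197 = 57%) |
| 2 | 29 + 28 = Day 57 | 197 − 57 = 140 (140/197 = 71%) |
| 1 | 1 + 28 = Day 29 | 197 − 29 = 168 (168/197 = 85%) |

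A participant who stops early therefore has the shortest tabulated window. After Week 28, a further 364 − 197 = 167 days (Days 198 to 364) of SAE and index-knee special-interest collection fall wholly outside the tables.

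For by-visit summaries, the earliest Week 16 visit is 113 − 7 = Day 106, which is 106 − 85 = 21 days past the close. Protocol 4.6.2 has vital signs taken at every study visit, so the Week 16 and Week 28 values would drop out. The same reasoning applies to any laboratory or ECG assessment scheduled after Day 85. Table 8-1 as supplied does not allow those marks to be matched to visits, so I use vital signs as the example.

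For worsened events, take a condition present before Day 1 that becomes more severe on Day 40. Protocol 12.5.2 and SAP 5.1 count it. SAP 3.2 and SAP 5 ask for a start date between Day 1 and Day 85, so it is counted only if the worsening is entered as a new record. The documents do not say whether it is.

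**The case against.** The strongest defence is that a 28-day window is a legitimate choice in an exploratory study and nothing is discarded. All safety data are listed, later data are flagged, and all deaths are listed. With about 13 to 15 participants per arm, the listings can be read by eye. The tolerability signal that led to the hold followed dosing, and the hsCRP rises in the first-in-human study lasted under five days; events of that timing fall inside the window. This stands, and it is why the 28-day table may stay. It does not explain why the protocol's longer tabulation is dropped without visible comment, and small arms also make the extra counts cheap.

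A reader might infer several stronger points that the documents do not support:

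- That SAP 5.1 contradicts SAP 3.2 and 5 on the end date. SAP 5.1 sits under SAP 5, so its silence can be read as subject to the 28-day rule. The end-date conflict is with protocol 12.5.2. Within the SAP, the conflict concerns worsened events only.
- That 28 days breaches the protocol's follow-up minimum, "Adverse event monitoring should be continued for at least 30 days (or 5 half-lives or end of study visit, whichever is longer". That sentence governs monitoring and collection, not the analysis window.
- That the half-life shows the window to be too short. Five half-lives at 15 mg are 5 × 239 h = 1195 h = 49.8 days, reaching about Day 107. This is a single-dose plasma figure, the visible text gives none for 25 mg or repeated dosing, and the issue here is local tolerability. It is context only.
- That protocol 12.5.2 has no on-treatment concept. Its laboratory shift tables do compare baseline with the worst on-treatment value. Its AE tables and by-visit summaries carry no such limit.
- That no later-onset table exists anywhere. SAP Section 8 shows a heading without text, although the document history lists it as revised. Section 10, also listed as revised, is not visible, and the TFL shells are a separate document.

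**Conclusion.** The point holds and should be fixed, though it does not touch the primary analysis. As written, the SAP tabulates less than protocol 12.5.2 plans. AEs with a known onset from Day 86 have no by-arm count in the visible text. That is 112 of the 197 days of all-AE collection after three doses, and all of the Week 28 to 52 collection of SAEs and index-knee AEs of special interest. Worsened pre-existing events are treated inconsistently, and later visits would fall out of the by-visit summaries.

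The sizes assume on-schedule dosing and visits. They are shares of calendar time, not of events: they do not say that 57% of AEs would be missed, and onset may well cluster soon after injections. Events whose incomplete dates prevent classification default to on-treatment, so a few later ones could enter the tables. The wording of the cut is certain. The absence of a later-onset table is certain only for the text supplied.

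**What to change.** In the SAP:

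1. Use one treatment-emergent definition in 3.2, 5 and 5.1, with its end stated, that includes pre-existing events that worsen.
2. Keep the 28-day AE table if wanted, and add a by-arm table of post-treatment AEs to Week 28.
3. Add a separate by-arm table of SAEs and index-knee AEs of special interest to Week 52. Keep it separate because AE collection narrows after Week 28. Produce it once Week 52 data are complete: SAP 3.1 times the final analysis to when all participants have the primary endpoint, whereas protocol 12 places it after end of study.
4. State that by-visit laboratory, vital-sign and ECG summaries cover every scheduled post-dose visit at which the data are collected. SAP 5.4.1 assigns no treatment to ECGs taken more than 30 days after the last dose, so that rule would need to change with it.
5. Record any remaining departure from protocol 12.5.2 in SAP Section 8. If the TFL shells already hold these tables, say so in the SAP.

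The cost is SAP text, a changed date cut in existing programs and two further AE tables. No new data are needed. The downside is more unrelated background AEs in the tables and slightly more programming.
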